8.5.2 Analysis of the secondary variable(s)

Secondary efficacy variables;

The change from baseline in core set measures of ACR and DAS28 will be analyzed with an ANCOVA model approach using PROC MIXED in SAS with baseline value as covariate.

8.5.2.1 Pharmacokinetic analyses

The derivation of the PK parameters will be performed at Covance (Clinical Pharmacokinetic Alliance). The PK parameters will be derived using non-compartmental methods with Phoenix® WinNonlin® Version 6.3, or higher (Pharsight Corp., Mountain View, California), in accordance with “Best Practice Reference Guidelines Pharmacokinetic Evaluations in Clinical Studies”. All descriptive statistical computations will be performed using SAS Version 9.2, or higher.

Where possible, the following PK parameters will be assessed for AZD9567 and prednisolone.

$AUC_{(0-24)}$	Area under the plasma concentration-time curve from time zero to 24 hours after administration (using the pre-dose value as the 24 h time point)
$AUC_{(0-\text{last})}$	Area under the plasma concentration-time curve from time zero to the time of the last quantifiable concentration
$AUC_{(0-6)}$	Area under the plasma concentration-time curve from time zero to 6 h after administration
t_{\max}	Time to reach maximum plasma concentration
C_{\min}	Predose concentration

Additional PK parameters may be determined where appropriate.

Further details regarding the calculation and descriptive statistics of the PK parameters will be described in the SAP.

8.5.3 Subgroup analysis (if applicable)

Exploratory analyses may be performed where subgroups of interest have been identified and depending on the numbers of subjects within each subgroup.

8.5.4 Sensitivity analysis (if applicable)

To be confident in the results of the study, we need to check that the assumptions of the performed analyses are compatible with the data at hand. Therefore, sensitivity analysis is required. This can concern (but is not restricted to) issues related to choice of the method of analysis, handling of missing data, simplifying assumptions such as ignoring correlations and interaction terms or handling of outliers. A more detailed description of sensitivity analysis will be included in the SAP.

8.5.5 Exploratory analysis (if applicable)

Exploratory and post hoc analyses may be performed to answer additional questions.

9. STUDY AND DATA MANAGEMENT BY ASTRAZENECA

9.1 Training of study site staff

Before the first subject is entered into the study, an AstraZeneca representative will review and discuss the requirements of the Clinical Study Protocol and related documents with the investigational staff and also train them in any study specific procedures and the WBDC system(s) utilised.

The Principal Investigator will ensure that appropriate training relevant to the study is given to all of these staff, and that any new information relevant to the performance of this study is forwarded to the staff involved.

The Principal Investigator will maintain a record of all individuals involved in the study (medical, nursing and other staff).

9.2 Monitoring of the study

During the study, an AstraZeneca representative will have regular contacts with the study site, including visits to:

- Provide information and support to the Investigator(s)
- Confirm that facilities remain acceptable
- Confirm that the investigational team is adhering to the Clinical Study Protocol, that data are being accurately and timely recorded in the CRFs, that biological samples are handled in accordance with the Laboratory Manual and that study drug accountability checks are being performed
- Perform source data verification (a comparison of the data in the CRFs with the subject's medical records at the hospital or practice, and other records relevant to the study) including verification of informed consent of participating subjects. This will require direct access to all original records for each subject (e.g., clinic charts)
- Ensure withdrawal of informed consent to the use of the subject's biological samples is reported and biological samples are identified and disposed of/destroyed accordingly, and the action is documented, and reported to the subject.

The AstraZeneca representative will be available between visits if the Investigator(s) or other staff at the centre needs information and advice about the study conduct.

9.2.1 Source data

Refer to the Clinical Study Agreement for location of source data.

9.2.2 Study agreements

The Principal Investigator at each/the centre should comply with all the terms, conditions, and obligations of the Clinical Study Agreement, or equivalent, for this study. In the event of any inconsistency between this Clinical Study Protocol and the Clinical Study Agreement, the terms of Clinical Study Protocol shall prevail with respect to the conduct of the study and the treatment of subjects and in all other respects, not relating to study conduct or treatment of subjects, the terms of the Clinical Study Agreement shall prevail.

Agreements between AstraZeneca and the Principal Investigator should be in place before any study-related procedures can take place, or subjects are enrolled.

9.2.3 Archiving of study documents

The Investigator follows the principles outlined in the Clinical Study Agreement (CSA).

9.3 Study timetable and end of study

The end of the study is defined as ‘the last visit of the last subject undergoing the study’.

The study may be terminated at individual centres if the study procedures are not being performed according to GCP, or if recruitment is slow. AstraZeneca may also terminate the entire study prematurely if concerns for safety arise within this study or in any other study with AZD9567.

9.4 Data management by AstraZeneca or delegate

Data management will be performed by IQVIA, according to the Data Management Plan.

The data collected through third party sources will be obtained and reconciled against study data.

Adverse events and medical/surgical history will be classified according to the terminology of the latest version the Medical Dictionary for Regulatory Activities (MedDRA). Medications will be classified according to the WHO Drug Dictionary. All coding will be performed by the Medical Coding Team at IQVIA.

Data queries will be raised for inconsistent, impossible or missing data. All entries to the study database will be available in an audit trail.

The data will be validated as defined in the Data Management Plan. Quality control procedures will be applied to each stage of data handling to ensure that all data are reliable and have been processed correctly. The Data Management Plan will also clarify the roles and responsibilities of the various functions and personnel involved in the data management process.

When all data have been coded, validated, signed and locked, clean file will be declared. Any treatment revealing data may thereafter be added and the final database will be locked.

Serious Adverse Event (SAE) Reconciliation

SAE reconciliation reports are produced and reconciled with the Patient Safety database and/or the investigational site.

Data Management of genotype data

Any genotype data generated in this study will be stored in the AstraZeneca genotyping LIMS database, or other appropriate secure system within AstraZeneca and/or any other organization contracted to work with AstraZeneca to analyse samples. The results from this genetic research may be reported in the CSR for the main study, or in a separate report as appropriate.

Data associated with human biological samples

Data associated with biological samples will be transferred from laboratory (ies) internal or external to AstraZeneca.

10. ETHICAL AND REGULATORY REQUIREMENTS

10.1 Ethical conduct of the study

The study will be performed in accordance with ethical principles that have their origin in the Declaration of Helsinki and are consistent with ICH/Good Clinical Practice, applicable regulatory requirements and the AstraZeneca policy on Bioethics and Human Biological Samples.

10.2 Subject data protection

The Informed Consent Form will incorporate (or, in some cases, be accompanied by a separate document incorporating) wording that complies with relevant data protection and privacy legislation.

AstraZeneca will not provide individual genotype results to subjects, any insurance company, any employer, their family members, general physician, unless required to do so by law.

Precautions are taken to preserve confidentiality and prevent genetic data being linked to the identity of the subject. In exceptional circumstances, however, certain individuals might see both the genetic data and the personal identifiers of a subject. For example, in the case of a medical emergency, an AstraZeneca Physician or an Investigator might know a subject's identity and also have access to his or her genetic data. Also Regulatory authorities may require access to the relevant files, though the subject's medical information and the genetic files would remain physically separate.

10.3 Ethics and regulatory review

An Ethics Committee should approve the final Clinical Study Protocol, including the final version of the Informed Consent Form and any other written information and/or materials to be provided to the subjects. The Investigator will ensure the distribution of these documents to the applicable Ethics Committee, and to the study site staff.

The opinion of the Ethics Committee should be given in writing. The Investigator should submit the written approval to AstraZeneca before enrolment of any subject into the study.

The Ethics Committee should approve all advertising used to recruit subjects for the study.

AstraZeneca should approve any modifications to the Informed Consent Form that are needed to meet local requirements.

If required by local regulations, the Clinical Study Protocol should be re-approved by the Ethics Committee annually.

Before enrolment of any subject into the study, the final Clinical Study Protocol, including the final version of the Informed Consent Form, is approved by the national regulatory authority or a notification to the national regulatory authority is done, according to local regulations.

AstraZeneca will handle the distribution of any of these documents to the national regulatory authorities.

AstraZeneca will provide Regulatory Authorities, Ethics Committees and Principal Investigators with safety updates/reports according to local requirements.

10.4 Informed consent

The Principal Investigator(s) at each centre will:

- Ensure each subject is given full and adequate oral and written information about the nature, purpose, possible risk and benefit of the study
- Ensure each subject is notified that they are free to discontinue from the study at any time
- Ensure that each subject is given the opportunity to ask questions and allowed time to consider the information provided
- Ensure each subject provides signed and dated informed consent before conducting any procedure specifically for the study
- Ensure the original, signed Informed Consent Form(s) is/are stored in the Investigator's Study File
- Ensure a copy of the signed Informed Consent Form is given to the subject

- Ensure that any incentives for subjects who participate in the study as well as any provisions for subjects harmed as a consequence of study participation are described in the informed consent form that is approved by an Ethics Committee.

10.5 Changes to the Clinical Study Protocol and Informed Consent Form

Study procedures will not be changed without the mutual agreement of the International co-ordinating Investigator, National Co-ordinating Investigator and AstraZeneca.

If there are any substantial changes to the Clinical Study Protocol, then these changes will be documented in a new version of the study protocol.

The new version of the Clinical Study Protocol is to be approved by the relevant Ethics Committee and if applicable, also the national regulatory authority approval, before implementation. Local requirements are to be followed for new versions of Clinical Study Protocols.

AstraZeneca will distribute any new versions of the Clinical Study Protocol to each Principal Investigator(s). For distribution to Ethics Committee see Section [10.3](#).

If a change to a Clinical Study Protocol requires a change to a centre's Informed Consent Form, AstraZeneca and the centre's Ethics Committee are to approve the revised Informed Consent Form before the revised form is used.

10.6 Audits and inspections

Authorised representatives of AstraZeneca, a regulatory authority, or an Ethics Committee may perform audits or inspections at the centre, including source data verification. The purpose of an audit or inspection is to systematically and independently examine all study-related activities and documents, to determine whether these activities were conducted, and data were recorded, analysed, and accurately reported according to the Clinical Study Protocol, Good Clinical Practice (GCP), guidelines of the International Conference on Harmonisation (ICH), and any applicable regulatory requirements. The Investigator will contact AstraZeneca immediately if contacted by a regulatory agency about an inspection at the centre.

HPA	Hypothalamic–pituitary–adrenal
IARA	Investigator's Global Assessment of RA
ICH	International Committee on Harmonisation
ITT	Intent-to-treat
i.v.	Intravenous
LLOQ	Lower limit of quantification
LPS	Lipopolysaccharide
MCP	Metacarpophalangeal joints
MedDRA	Medical Dictionary for Regulatory Activities
MMRM	Mixed model repeated measures
NQ	Non-quantifiable
PD	Pharmacodynamic analysis set
PGx	Pharmacogenetics
PIP	Proximal interphalangeal
PK	Pharmacokinetic
PP	Per protocol analysis set
PT	Preferred term
RA	Rheumatoid arthritis
RNA	Ribonucleic acid
RND	All subjects randomised analysis set
SAE	Serious adverse event
SAF	Safety analysis set
SARA	Subject's Assessment of Rheumatoid Arthritis
REML	Residual/restricted maximum likelihood
s.c	Subcutaneous
SJC 66	Swollen joint count 66
SOC	System organ class

Abbreviation or special term	Explanation
t _{1/2z}	Half-life associated with the terminal slope (λz) of the semi-logarithmic concentration time curve
TEAE	Treatment emergent adverse event
TJC 68	Tender joint count 68
t _{max}	Time point of the maximal plasma concentration of a drug
TNF α	Tumour necrosis factor alpha
VAS	Visual Analogue Scale

1. STUDY DETAILS

1.1 Study objectives

1.1.1 Primary objective

The primary objective of this study is to assess the efficacy of AZD9567 40 mg, compared to Prednisolone 20 mg in subjects with active rheumatoid arthritis (RA) in spite of stable treatment with conventional and/or subcutaneous (s.c)/ intravenous (i.v.) biological disease-modifying anti-rheumatic drugs (DMARDs) by assessment of:

- Change from baseline (CFB) in 28 joints Disease Activity Score (DAS28) using C-reactive protein (DAS28 - CRP) after 14 days of treatment at Day 15.

1.1.2 Secondary objectives

The secondary objectives of this study after approximately two weeks treatment period are:

- To further assess the efficacy of AZD9567 40 mg, compared to Prednisolone 20 mg in subjects with active RA in spite of stable treatment with conventional and/or s.c/i.v. biological DMARDs by assessment of:
 - Proportion of subjects achieving American College of Rheumatology (ACR) 20, 50 and 70 responses.
 - Change from baseline in Swollen Joint Count 66 (SJC 66).
 - Change from baseline in Tender Joint Count 68 (TJC 68).
 - Change from baseline in individual components of:
 - DAS28 (number of swollen and tender joints 28, subject's assessments of global disease activity (GH) and CRP).
 - ACR response criteria (number of swollen joints 66 and tender joints 68, subject's assessments of global disease activity (GH), physician's global assessment of disease activity, subject's assessments of pain, subject's assessments of physical function and CRP).
- To evaluate the pharmacokinetic (PK) profile of AZD9567 in subjects with active RA in spite of stable treatment with conventional and/or s.c/i.v. biological DMARDs by assessment of:
 - PK parameters including area under the plasma concentration-time curve until the last quantifiable concentration AUC(last), area under the concentration-time curve from time zero to 24 hours after dose AUC(0-24), area under the concentration-time curve from time zero to 6 hours after dose AUC(0-6), maximum plasma concentration during a dosing interval (Cmax), time to reach

maximal plasma concentration (t_{max}) the last plasma concentration measured before the last dose (C_{trough}) and apparent plasma clearance (CL/F).

1.1.3 Safety objective

To assess the safety and tolerability of AZD9567 in subjects with active RA in spite of stable treatment with conventional and/or s.c/i.v. biological DMARDs by assessment of:

- Adverse events (AEs).
- Vital signs.
- Electrocardiogram (ECG).
- Laboratory parameters (haematology, clinical chemistry and urine).

1.1.4 Exploratory objectives

The exploratory objectives of this study after approximately two weeks treatment period are:

- To assess the responses to AZD9567 of relevant biomarkers. Whole blood and serum/plasma will be collected to enable relevant analyses such as, effects on bone, metabolism and hypothalamic–pituitary–adrenal (HPA) axis by assessment of exploratory blood biomarkers:
 - Lipopolysaccharide (LPS) stimulated tumour necrosis factor alpha (TNF α).
 - Plasma cortisol.
 - Other possible exploratory biomarkers including RNA.
- Exploratory biomarker variables will be reported in a separate biomarker report and will not be included in the clinical study report (CSR) unless something clinically important is observed, with the exception of plasma cortisol which will be analysed and reported in the

CSR. TNF α planned analyses will be described in this SAP but will be reported separate to the CSR.

- European League Against Rheumatism (EULAR) response criteria.
- DAS28 remission.
- Clinically important change in DAS28 score.
- Low disease activity based on DAS28 score.

The following exploratory objective is outside the scope of this SAP and will be presented in a separate report:

- To evaluate the PK profile of Prednisolone in subjects with active RA in spite of stable treatment with conventional and/or s.c./i.v. biological DMARDs.

The following exploratory objective is outside the scope of this SAP and will not be included in the clinical study report (CSR), unless something clinically important is observed:

- To obtain optional blood samples for future pharmacogenetic (PGx) research aiming to identify/explore pharmacodynamic biomarkers or genetic variations that may affect the efficacy, pharmacodynamics, safety and tolerability profile related to AZD9567 treatment by assessment of:
 - Deoxyribonucleic acid (DNA) from whole blood.

1.2 Study design

This is a Phase 2a, randomised, double-blind, double dummy, parallel study to assess the efficacy, safety and tolerability of AZD9567 40mg compared to Prednisolone 20 mg in subjects with active RA in spite of stable treatment with conventional or biological DMARDs.

At Visit 1 (screening visit) eligible subjects will be identified. Subjects will be asked to provide informed consent after which screening assessments will be performed.

At Visit 2, eligible subjects with established RA and moderate to high disease activity as defined by ACR Guidelines (DAS28 > 3.2) will be randomised in a ratio 1:1 to take either AZD9567 40 mg or Prednisolone 20 mg for 14 days once daily. Since this study is double-blind and AZD9567 and Prednisolone are different formulations (oral suspension and capsules respectively), all subjects will have to take both formulations every day (active AZD9567 + placebo to Prednisolone or placebo to AZD9567 + active Prednisolone).

[figure not shown]
A telephone call to check subject well-being will be termed Visit 3.

Visit 4 will occur approximately 7 days after Visit 2, and Visit 5, which is the end-of-treatment visit, will occur approximately 14 days after Visit 2.

A follow-up visit (Visit 6) will be performed approximately 14 days after last study treatment dose (at Visit 5) to ensure the safety and well-being of subjects.

For more information regarding the visits and time windows refer to the study flowchart, [Figure 1](#).

Figure 1 Study flow Chart

R: Randomised to study treatment

1.3 Number of subjects

It is planned to randomise approximately 40 subjects in total, 20 subjects to each treatment group. It is anticipated that approximately 80-100 subjects will need to be screened in order to achieve randomisation total. Planned recruitment of subjects will take place across 7 sites in 2 countries (Sweden and Netherlands).

The main analysis will be based on the difference in the mean CFB for AZD9567 and the mean CFB of prednisolone.

The details of the sample size calculation are based on internal decision criteria as explained in Frewer et al, 2016. In these calculations we use the reliability threshold of the DAS28 index known to be 0.6 (Siemons et al, 2014).

A sample size of n=10 per group was agreed on however is not sufficiently powered to support hypothesis testing.

2. ANALYSIS SETS

2.1 Definition of analysis sets

The following analysis sets will be used in this study:

2.1.1 All subjects enrolled (ENR) analysis set

The all subjects enrolled (ENR) set will contain all subjects who signed informed consent prior to performing any specific study-related procedures.

2.1.2 All subjects randomised (RND) analysis set

The all subjects randomised (RND) analysis set will contain all subjects in the ENR analysis set and who were randomised to one of the two treatment groups. The all subjects randomised analysis set will be analysed according to their planned treatment arm, regardless of the actual treatment received.

2.1.3 Safety analysis set (SAF)

The safety analysis set (SAF) will include all subjects randomised and received at least one dose of study treatment. The SAF will be analysed according to the actual treatment received, regardless of the randomised treatment assigned.

2.1.4 Full analysis set (FAS)

The primary analysis variable for efficacy will be analysed using the full analysis set (FAS). The FAS, will include all subjects randomised and received at least one dose of study treatment. In accordance with International Committee on Harmonisation (ICH) E9, the FAS will be analysed using the Intent-to-treat (ITT) principle, which is the analysis on planned treatment arm, regardless of actual treatment received. The SAF and FAS will have the same set of subjects but will be analysed differently according to actual vs. planned.

2.1.5 Per protocol (PP) analysis set

The PP analysis set will include subjects from the FAS who:

- Did not have an important protocol deviation that are considered to have an impact on the analysis of the primary endpoints;
- Completed the study.

The PP analysis set will be analysed according to the actual treatment received, regardless of the planned treatment.

Criteria for exclusion from the PP analysis set will be documented in a separate analysis sets and PDs plan.

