8.3 Definitions of analysis sets

8.3.1 Efficacy analysis set

The primary analysis population for efficacy will be analyzed using the intention to treat (ITT) population. This is in accordance to the ICH E9 guideline suggesting that the analysis of the primary endpoint should be analyzed according to the treatment to which patients were actually randomised. The ITT population will include all patients who were randomised and received at least one dose of study medication. Patients will be analyzed according to the treatment to which they were intended to be randomised to. ITT is sometimes referred to as Full Analysis Set.

Moreover, the primary analysis population for efficacy will also be analyzed using the Per Protocol (PP) population which includes all patients who were randomised, treated with study medication and did not have a major protocol deviation. Major protocol deviations leading to exclusion from the PP population will be finalized prior to un-blinding during the blind data review meeting. Full criteria for exclusion from the analysis set will be detailed in the Statistical Analysis Plan (SAP).

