4.3.1 Primary efficacy statistical model

Formal statistical testing will be performed for exploratory purposes only.

The default significant level will be two-sided 5%, CIs will be 95% and all tests will be two-sided, unless otherwise specified in the description of the analyses. Two-sided p -value ≤ 0.05 will be considered statistically significant.

Confidence intervals (CIs) for the true difference in means, $\mu_{\text{AZD9567}} - \mu_{\text{Prednisolone}}$, will be calculated using the estimated treatment effect and the mean square error.

A MMRM is to be used to examine the primary efficacy variable, using the PROC MIXED procedure in SAS.

The MMRM model will include the baseline DAS28 score as a covariate.

The MMRM model will include categorical fixed effects of treatment, visit, treatment-by-visit interaction and country:

- Change from baseline (at Day 15) = Treatment group baseline DAS28 score Treatment group*visit
- Treatment group = AZD9567 or Prednisolone.
- Visit = Day 8 and Day 15.
- Country = Netherlands or Sweden
- Change from baseline (at Day 15) = Change in DAS28 from baseline at Day 15.

An unstructured matrix for the within-subject error variance covariance will be used. The denominator degrees of freedom will be calculated according to the Kenward-Roger method.

In case of non-convergence of the preferred model or memory space issues the following models will be explored in the order given:

1. Country may be removed from the model.
2. The second backup model is the same as the preferred model but the Kenward-Roger method will be replaced by Satterthwaite approximation.

The least squares mean (LSM) change from baseline in DAS28 score and corresponding standard error (SE) and 95% confidence interval (CI) by treatment group at Day 8 and Day 15 will be provided in a table. The least squares mean difference (LSMD) between the two

treatment groups at Day 8 and Day 15 and corresponding 95% CI and two-sided p-value will also be presented in the table.

A figure will be provided displaying the LSM change from baseline by treatment group and visit, along with the 95% CI.

The FAS and PP analysis sets will be used for primary efficacy with FAS analysis set as primary interest.

Results for the PP analysis will be tabulated and displayed graphically in the same manner as the primary analysis.

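### The SAP's per-protocol set requires study completion, so it can discard valid Day 15 data for an event after the endpoint

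*SAP*

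**What the plan says.** Protocol 8.3.1 describes a PP set that "includes all patients who were randomised, treated with study medication and did not have a major protocol deviation". Completion is not mentioned, and the same section leaves the complete list of exclusions to the SAP.

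SAP 2.1.5 starts from the FAS and sets two conditions. The first is that the patient "Did not have an important protocol deviation that are considered to have an impact on the analysis of the primary endpoints". The second stands alone: "Completed the study". The section then passes the detail on: "Criteria for exclusion from the PP analysis set will be documented in a separate analysis sets and PDs plan". That plan is not among the documents.

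On timing, SAP 1.1.1 places the primary outcome "after 14 days of treatment at Day 15", and the primary model in SAP 4.3.1 has "Visit = Day 8 and Day 15". SAP 4.3.2 compares ACR responses in the FAS and PP sets at the same two days. Visit 6 is the last visit in the protocol's Table 1. SAP 1.2 describes it as a follow-up for safety and well-being, and SAP 3.2.1 notes that patients are then two weeks off treatment.

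**The concern.** The two PP conditions pull against each other. The first removes a patient only for a deviation that matters to the primary endpoint. The second removes a patient for not finishing the study, whether or not the endpoint was affected. If finishing the study includes Visit 6, a patient with full Day 8 and Day 15 assessments and no relevant deviation is lost because of something that happened, or did not happen, in the two weeks after the endpoint was measured.

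The stated aim is equivalence to prednisolone, and PP is the only other analysis set named for the primary variable. A reader will look to it to see whether the FAS result holds up. With 10 patients per group and no replacement of withdrawals (Protocol 3.10.3), each needless exclusion is a tenth of an arm.

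**Working it through.** **What completion means.** Neither document defines it for a patient. Two things point to Visit 6. It is the last scheduled visit in Table 1, and the disposition categories in SAP 4.8.1 count completion of the study separately from completion of study treatment. So the criterion, as worded, is not treatment completion. This is a strong inference, not a written rule.

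**Whether any PP analysis needs Visit 6.** The specified PP analyses are DAS28 by MMRM (SAP 4.3.1) and ACR20/50/70 (SAP 4.3.2), all at Day 8 and Day 15. DAS28, ACR and joint counts are also collected at Visit 6, and the exploratory DAS28 summaries run to Day 28 (SAP 4.3.3.5). SAP 4.3.2 assigns exploratory efficacy endpoints to the FAS unless otherwise stated. No specified PP analysis uses Visit 6.

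**Precision.** The plan gives no figure for this. The input is 10 per group (SAP 1.3). For a simple difference in means with common SD, the SE is proportional to √(1/n₁ + 1/n₂), so the ratio to the full set is √[(1/n₁ + 1/n₂) / (2/10)]:

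- one patient lost from one arm (9 and 10): √(0.2111/0.2) = 1.027, up 2.7%
- one lost from each arm (9 and 9): √(0.2222/0.2) = 1.054, up 5.4%
- two lost from each arm (8 and 8): √(0.25/0.2) = 1.118, up 11.8%

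These apply to lost patients who have a Day 15 value. A patient who left before Day 15 would have contributed only Day 8 data through the MMRM, so the loss is smaller.

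**Possible bias (illustration only).** The documents give neither an SD nor a dropout rate. I assume an SD of change of 0.6 to 1.2 DAS28 units. Suppose a share q of one arm does not complete, and that non-completion has correlation ρ with a poor Day 15 change. That arm's PP mean then moves by about ρ × SD × φ(z₁₋q)/(1 − q), a large-sample formula. The factor φ/(1 − q) is 0.195 for q = 10% and 0.35 for q = 20%.

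- q = 10%, ρ = 1: 0.195 × 0.6 = 0.12 to 0.195 × 1.2 = 0.23
- q = 20%, ρ = 1: 0.35 × 0.6 = 0.21 to 0.35 × 1.2 = 0.42
- ρ = 0.5: half of each
- ρ = 0: no bias, only the loss of precision

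For scale, Protocol 8.2 uses a 0.6-unit reliability threshold and Protocol 8.5.1 a decision bound of size 0.4. The sign depends on the arm. Losing the poorest responders from the AZD9567 arm shifts the PP difference in its favour, losing them from the prednisolone arm shifts it the other way, and equal losses roughly cancel.

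**The case against.** **The protocol told the SAP to set these criteria.** It did. A reader might infer an undisclosed departure from the protocol because the table of changes in SAP Section 6 is silent. Given that delegation, the silence is weak evidence of a fault, and the point does not rest on it.

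**The separate plan may define completion.** It may, and it might define it relative to Day 15. That cannot be assumed, and the wording in SAP 2.1.5 would still need correcting.

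**Any PP set selects on events after randomisation.** True, and exclusion for protocol deviations does so too. What sets this criterion apart is that it selects on an event after the endpoint with no bearing on its measurement.

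**The consequence is limited.** This also stands. The FAS is of primary interest and keeps these patients, testing is exploratory, no decision rule is tied to the PP result, and the SAP says the study is not powered for hypothesis testing.

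Two stronger readings are tempting. One is that the criterion makes the arms look more alike. That would require poor responders to be lost mainly from the worse arm, and nothing in the documents says so. The other is that everyone who stops for an adverse event is excluded. Protocol 3.9.1 and 3.10.3 separate stopping the drug from withdrawing from the study, so a patient who stops the drug but attends every visit can still complete.

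**Conclusion.** The point holds as a defect in the PP definition. On the natural reading, SAP 2.1.5 removes patients with complete Day 8 and Day 15 data for an event after the endpoint, against the logic of its own first condition. It rests on one inference, that missing Visit 6 counts as not completing the study.

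The cost in precision is 2.7%, 5.4% or 11.8% on the SE for one patient, one per arm or two per arm, where those patients have Day 15 data. Bias is possible, but its size and direction are unknown. The illustrative shifts depend wholly on the assumed SD, dropout share and correlation, and vanish if non-completion is unrelated to response. The effect is confined to the PP analyses of DAS28 and ACR. It is worth correcting, but it does not threaten the primary analysis.

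**What to change.** Before unblinding, delete the completion condition from SAP 2.1.5. The MMRM then keeps patients with full Day 15 data, and also the Day 8 data of early leavers who have no important deviation. One consequence should be accepted knowingly: under SAP 4.4.3 such early leavers would count as ACR non-responders at Day 15 in the PP analysis, as they already do in the FAS.

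At the least, replace the condition with a requirement for a baseline and a Day 15 DAS28-CRP. This ties the set to the endpoint but still excludes patients who leave before Day 15, so it removes only part of the selection.

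Make the same change in the separate analysis-sets plan. Deletion alone should not be described as restoring the definition in Protocol 8.3.1. The SAP also narrows the deviations to those affecting the primary endpoint and analyses the PP set by treatment actually received. The cost is one line in each document, with no new data and no effect on the FAS.
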